6. STUDY POPULATION

Prospective approval of protocol deviations to recruitment and enrolment criteria, also known as protocol waivers or exemptions, is not permitted.

6.1. Inclusion Criteria

Participants are eligible to be included in the study only if all of the following criteria apply:

Age

1. Participant must be 18 to 55 years of age inclusive, at the time of signing the informed consent.

Type of Participant and Disease Characteristics

2. Participants who are overtly healthy as determined by medical evaluation including medical history and psychiatric history, physical examination, laboratory tests, and 24 h Holter monitoring.

Weight

3. Body weight $\geq 50.0\text{kg}$ (110lbs.) for men and $\geq 45.0\text{kg}$ (99lbs) for women and body mass index (BMI) within the range 18.5-32.0 kg/m^2 (inclusive).

Sex

4. Male or female

a. Male participants:

A male participant must agree to use contraception as detailed in [Appendix 5](#) of this protocol during the treatment period and for at least 14 weeks following the last dose, corresponding to the time needed to eliminate study treatment for potential genotoxic and teratogenic study treatments *plus* an additional 90 days (spermatogenesis cycle). In addition, male participants must refrain from donating sperm during this period.

b. Female participants:

A female participant is eligible to participate if she is not a woman of childbearing potential (WOCBP) as defined in [Appendix 5](#).

Informed Consent

5. Capable of giving signed informed consent as described in [Appendix 3](#) which includes compliance with the requirements and restrictions listed in the informed consent form (ICF) and in this protocol.

6.2. Exclusion Criteria

Participants are excluded from the study if any of the following criteria apply:

Medical Conditions

1. Alanine transaminase (ALT) >1.5x upper limit of normal (ULN)
2. Bilirubin >1.5xULN (isolated bilirubin >1.5xULN is acceptable if bilirubin is fractionated and direct bilirubin <35%).
3. Current or chronic history of liver disease, or known hepatic or biliary abnormalities.
4. Pre-existing clinically relevant, in the opinion of the PI, gastro-intestinal pathology or diagnosis – e.g. irritable bowel syndrome, inflammatory bowel disease, and/or significant baseline signs and symptoms.
5. Medical history of cardiac arrhythmias or cardiac disease or a family or personal history of long QT syndrome.
6. Any known or suspected pre-existing psychiatric condition
7. Any positive (abnormal) response confirmed by the investigator on a screening clinician (or qualified designee) administered CSSRS for either the SAD or MAD.
8. Any other clinical condition (including but not limited to active substance use) or prior therapy that, in the opinion of the Investigator, would make the participant unsuitable for the study; unable to comply with dosing requirements; or unable to comply with study visits; or a condition that could affect the absorption, distribution, metabolism or excretion of the drug.

Prior/Concomitant Therapy and Dietary Restriction

9. Unable to refrain from the use of prescription or non-prescription drugs (with the exception of paracetamol), including vitamins, herbal and dietary supplements (including St John's Wort) within 7 days (or 14 days if the drug is a potential enzyme inducer) or 5 half-lives (whichever is longer) prior to the first dose of study medication and for the duration of the study, unless in the opinion of the Investigator and VH Sponsor and Medical Monitor, the medication will not interfere with the study medications, procedures, or compromise participant safety (see Section 7.7).
10. Unwillingness to abstain from ingestion of any food or drink containing grapefruit and grapefruit juice, Seville oranges, blood oranges, or pomelos within 7 days prior to the first dose of study treatment(s) or until the end of the study.

Prior/Concurrent Clinical Study Experience

11. Participation in another concurrent clinical study or prior clinical study (with the exception of imaging trials) prior to the first dosing day in the current study: 30 days, 5 half-lives or twice the duration of the biological effect of the investigational product (whichever is longer).
12. Where participation in the study would result in donation of blood or blood products in excess of 500mL within 56 days.

Diagnostic assessments

13. Presence of hepatitis B surface antigen (HBsAg), or positive hepatitis C antibody test result at screening or within 3 months prior to first dose of study treatment.
14. A positive pre-study drug/alcohol screen.
15. A positive test for a diagnostic HIV-1 PCR
16. Exposure to more than four new chemical entities within 12 months prior to the first dosing day.
17. Exclusion criteria for screening ECG (a single repeat is allowed for eligibility determination):

	Males	Females
Heart rate	<45 or >100bpm	<50 or >100bpm
PR Interval	<120 or >220msec	
QRS duration	<70 or >120msec	
QTcF interval	>450msec	

Note: A heart rate from 100 to 110bpm can be rechecked by ECG or vitals within 30 minutes to verify eligibility.

18. Evidence of previous myocardial infarction (does not include ST segment changes associated with re-polarization).
19. Any conduction abnormality (including but not specific to left or right complete bundle branch block, AV block [2nd degree or higher], WPW syndrome).
20. Sinus Pauses >3 seconds.
21. Any significant arrhythmia which, in the opinion of the Investigator OR GSK/ViiV Medical monitor, will interfere with the safety for the individual participant.
22. Non-sustained or sustained ventricular tachycardia (≥ 3 consecutive ventricular ectopic beats).

Other Exclusions

23. History of regular alcohol consumption within 6 months of the study defined as: an average weekly intake of >14 units. One unit is equivalent to 8 g of alcohol: a half-pint (~240 mL) of beer, 1 glass (125 mL) of wine or 1 (25 mL) measure of spirits.
24. Regular use of tobacco- or nicotine-containing products within 3 months prior to screening.
25. History of sensitivity to any of the study medications, or components thereof or a history of drug or other allergy that, in the opinion of the Investigator or Medical Monitor, contraindicates their participation.

6.3. Lifestyle Restrictions

6.3.1. Meals and Dietary Restrictions

- Refrain from consumption of red wine, Seville oranges, grapefruit or grapefruit juice, pomelos, exotic citrus fruits, grapefruit hybrids, or their fruit juices from 7 days before the start of study treatment until after the final PK sample in the study.
- Unless otherwise indicated, all doses of GSK3640254 in this study will be administered in the fed state. The participants will fast for approximately 9.5 hours prior to dosing and will receive the moderate fat meal 30 minutes prior to dosing. Participants will eat this meal in 30 minutes or less. Dose administration will occur within 5 minutes of completion of meal consumption. Participants will not receive any further food until 4 hours post-dose. The moderate fat meal will contain about 600 calories with approximately 30% of them coming from fat.
- For food effect studies, water restrictions may be needed. No water is allowed from 2 hours prior to dosing until 2 hours after dosing except for the glass of water needed to administer the study medication (e.g. 240 mL). Water is allowed ad libitum at all other times.
- For the participants who may receive the study medication in fasted conditions, the participant will fast overnight (for at least 10 hours prior to dosing) and for an additional 4 hours after dosing.
- A snack and meal will be provided 4 hours and 10 hours, respectively, after dosing.
- Meals on Day -1 will follow the Day 1 schedule.

6.3.2. Drugs, Caffeine, Alcohol, and Tobacco

- During each dosing session, participants will abstain from ingesting caffeine- or xanthine-containing products (eg, coffee, tea, cola drinks, and chocolate) for 24 hours before admission to the unit (Day-2) until after collection of the final PK sample in each dosing session. Participants will be allowed to have caffeine or xanthine-containing products between dosing periods.
- During each dosing session, participants will abstain from alcohol for 24 hours before admission to the unit (Day-2) until after collection of the final PK sample in each dosing session. Participants will be allowed to have alcohol products between dosing periods up to less than 14 units per week.
- Use of tobacco products will not be allowed from screening until after the final follow-up visit.
- Subjects must have a negative drug test at screening and must abstain from recreational drug use from screening until after the final follow-up visit.

6.3.3. Activity

- Participants will abstain from strenuous exercise for 24 hours before each blood collection for clinical laboratory tests. Participants may participate in light recreational activities during studies (eg, watching television, reading).

6.4. Screen Failures

Screen failures are defined as participants who consent to participate in the clinical study but are not subsequently randomized. However, reserve participants only need to undergo the screening process once every 90 days; additionally, reserve participants will still be subject to Day -2 and -1 evaluations in routine fashion (as shown in the **SoA** table). A minimal set of screen failure information is required to ensure transparent reporting of screen failure participants to meet the Consolidated Standards of Reporting Trials (CONSORT) publishing requirements and to respond to queries from regulatory authorities. Minimal information includes demography, screen failure details, eligibility criteria that established screen failure, and any serious adverse events (SAEs).

Individuals who do not meet the criteria for participation in this study (screen failure) may not be rescreened.

7. TREATMENTS

Study treatment is defined as any investigational treatment(s), marketed product(s), placebo, or medical device(s) intended to be administered to a study participant according to the study protocol.

7.1. Treatments Administered

Study Treatment Name:	GSK3640254	Placebo
Dosage formulation:	capsule	capsule
Unit dose strength(s):	1mg, 10mg, 100mg	placebo
Route of Administration	oral	oral
Dosing instructions:	Study medication will be administered by the study personnel during each dosing day with approximately 240 mL of water	Study medication will be administered by the study personnel during each dosing day with approximately 240 mL of water
Packaging and Labelling	Study Treatment will be provided in HDPE bottles. Each bottle will be labelled as required per country requirement.	Study Treatment will be provided in HDPE bottles. Each bottle will be labelled as required per country requirement.
Manufacturer	GSK, Harlow, UK	GSK, Harlow, UK

7.2. Dose Modification

The decision to proceed to the next dose level in both Part 1 (SAD) and Part 2 (MAD) will be made by the VH/GSK study team and study investigator based on safety, tolerability, and preliminary PK data obtained from the prior dose level(s).

7.3. Method of Treatment Assignment

Subjects will be assigned to study treatment in accordance with the randomization schedules generated by Clinical Statistics, prior to the start of the study, using validated internal software.

Each subject scheduled to receive study drug will receive a treatment allocation number when randomized. Study treatment will be dispensed at the study visits summarized in [\(SoA\)](#).

7.4. Blinding

This will be a double-blind study with participants and the site staff blinded. The sponsor will be unblinded (meaning those staff may have access to unblinded data). For dose escalation, the VH/GSK study team physicians, statistician, and clinical pharmacokinetic staff will have access to unblinded data and present data at dose escalation meetings in a blinded fashion when interacting with site staff. Other VH/GSK staff will remain blinded unless unblinding becomes necessary. The blind may be broken if, in the opinion of the investigator, it is in the participant's best interest for the investigator to know the study treatment assignment. The VH/GSK study team must be notified before the blind is broken unless identification of the study treatment is required for a medical emergency in which the knowledge of the specific blinded study treatment will affect the immediate management of the participant's condition. In this case, the VH/GSK study team must be notified within 24 hours after breaking the blind. The date and reason that the blind was broken must be recorded in the source documentation and CRF, as applicable.

Participants will be randomized in a 3:1 ratio to receive study treatment (active drug:placebo) within a period or cohort. Investigators will remain blinded to each participant's assigned study treatment throughout the course of the study.

Unblinded monitors and in the event of a Quality Assurance audit, the auditor(s) will be allowed access to un-blinded study treatment records at the site(s) to verify that randomization/dispensing has been done accurately.

A participant will be withdrawn if the participant's treatment code is unblinded by the investigator or treating physician. The primary reason for discontinuation (the event or condition which led to the unblinding) will be recorded in the CRF.

GSK's Global Clinical Safety and Pharmacovigilance (GCSP) staff may unblind the treatment assignment for any participant with an SAE. If the SAE requires that an expedited regulatory report be sent to one or more regulatory agencies, a copy of the report, identifying the participant's treatment assignment, may be sent to investigators in accordance with local regulations and/or GSK policy.

7.5. Preparation/Handling/Storage/Accountability

- The investigator or designee must confirm appropriate temperature conditions have been maintained during transit for all study treatment received and any discrepancies are reported and resolved before use of the study treatment.
- Only participants enrolled in the study may receive study treatment and only authorized site staff may supply or administer study treatment. All study treatments must be stored in a secure, environmentally controlled, and monitored (manual or automated) area in accordance with the labeled storage conditions with access limited to the investigator and authorized site staff.
- The investigator is responsible for study treatment accountability, reconciliation, and record maintenance (i.e., receipt, reconciliation, and final disposition records).

- Further guidance and information for the final disposition of unused study treatment are provided in the Study Reference Manual.
- Under normal conditions of handling and administration, study treatment is not expected to pose significant safety risks to site staff.
- A Material Safety Data Sheet (MSDS)/equivalent document describing occupational hazards and recommended handling precautions either will be provided to the investigator, where this is required by local laws, or is available upon request from GSK.
- Precaution will be taken to avoid direct contact with the study treatment. A Material Safety Data Sheet (MSDS) describing occupational hazards and recommended handling precautions will be provided to the investigator. In the case of unintentional occupational exposure notify the monitor, Medical Monitor and/or GSK study contact.

7.6. Treatment Compliance

- Participants will be dosed at the site and they will receive study treatment directly from the investigator or designee, under medical supervision. The date and time of each dose administered in the clinic will be recorded in the source documents. The dose of study treatment and study participant identification will be confirmed at the time of dosing by a member of the study site staff other than the person administering the study treatment. Study site personnel will examine each participant's mouth to ensure that the study treatment was ingested.

7.7. Concomitant Therapy

Any medication or vaccine (including over-the-counter or prescription medicines, vitamins, and/or herbal supplements) that the participant is receiving at the time of enrollment or receives during the study must be recorded along with:

- reason for use
- dates of administration including start and end dates
- dosage information including dose and frequency

The Medical Monitor should be contacted if there are any questions regarding concomitant or prior therapy.

Participants must abstain from taking prescription or non-prescription drugs (including vitamins and dietary or herbal supplements) within 7 days (or 14 days if the drug is a potential enzyme inducer) or 5 half-lives (whichever is longer) before the start of study treatment until completion of the follow-up visit, unless, in the opinion of the investigator and sponsor, the medication will not interfere with the study or is needed to ensure the participant's safety.

Paracetamol, at doses of ≤ 2 grams/day, is permitted for use at any time during the study.

7.8. Treatment after the End of the Study

Participants will not receive any additional treatment from VH/GSK, or with GSK3640254, after the completion of the study because only healthy volunteers are eligible for study participation.

8. DISCONTINUATION CRITERIA

8.1. Discontinuation of Study Treatment

A participant will be withdrawn from the study at any time:

- At his or her own request
- At the discretion of the Investigator or the Sponsor for safety (including lab abnormalities or intercurrent illness), psychiatric, compliance, or administrative reasons.
- Emergence of any positive (abnormal) response confirmed by the investigator on a clinician (or qualified designee) administered CSSRS during the on-treatment phase (MAD only)
- Any SAE.
- Termination of the study by GSK/VH. Safety data will be reviewed by the Sponsor in-stream by single case and collectively. If a safety concerns arises, a decision about continuation of the study will be made.
- Loss of ability to freely provide consent due to treatment of either a psychiatric or physical (eg, infectious disease) illness
- Unblinding by the PI for any reason
- Repeat non-adherence by the participant with the requirements of the protocol or treatment (as determined by Investigator in consultation with the Medical Monitor)

If the participant withdraws consent for disclosure of future information, the sponsor may retain and continue to use any data collected before such a withdrawal of consent.

If a participant withdraws from the study, he/she may request destruction of any samples taken and not tested, and the investigator must document this in the site study records.

If a participant withdraws from the study, he/she must complete a follow-up visit.

8.1.1. Liver Chemistry Stopping Criteria

Liver chemistry stopping and increased monitoring criteria have been designed to assure participant safety and evaluate liver event etiology (in alignment with the Food and Drug Administration [FDA] premarketing clinical liver safety guidance). These protocol guidelines are in alignment with FDA premarketing clinical liver safety guidance:

<http://www.fda.gov/downloads/Drugs/GuidanceComplianceRegulatoryInformation/Guidances/UCM174090.pdf>.

Discontinuation of study treatment for abnormal liver tests should be considered by the investigator when a participant has an ALT $\geq 3 \times$ ULN or if the investigator believes that it is in the best interest of the participant.

Details of liver safety follow-up procedures are described in [Appendix 7](#).

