8.1.2. QTc Stopping Criteria for Individual Participants

- The Fridericia QT correction formula (QTcF) *must* be used for *each individual participant* to determine eligibility for and discontinuation from the study. This formula may not be changed or substituted once the participant has been enrolled. Safety ECGs and other non-protocol specified ECGs are an exception.
- The QTc should be based on single or averaged QTc values of triplicate electrocardiograms obtained over a brief (e.g., 5-10 minute) recording period.
- A participant that meets either bulleted criterion below will be withdrawn from the study.
 - QTcF > 500msec,
 - Change from baseline: QTcF >60msec

See the [SoA](#) for data to be collected at the time of treatment discontinuation and follow-up and for any further evaluations that need to be completed.

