9. STUDY ASSESSMENTS AND PROCEDURES

- Study procedures and their timing are summarized in the [SoA](#).
- Protocol waivers or exemptions are not allowed
- Immediate safety concerns will be discussed with the sponsor immediately upon occurrence or awareness to determine if the participant will continue or discontinue study treatment.
- Adherence to the study design requirements, including those specified in the [SoA](#), is essential and required for study conduct.
- All screening evaluations must be completed and reviewed to confirm that potential participants meet all eligibility criteria. The investigator will maintain a screening log to record details of all participants screened and to confirm eligibility or record reasons for screening failure, as applicable.
- Procedures conducted as part of the participant's routine clinical management (eg, blood count) and obtained before signing of ICF may be utilized for screening or baseline purposes provided the procedure met the protocol-specified criteria and was performed within the time frame defined in the [SoA](#).
- The maximum amount of blood collected from each participant over the duration of the study, including any extra assessments that may be required, will not exceed 500 mL.
- Repeat or unscheduled samples may be taken for safety reasons or for technical issues with the samples.
- Time window allowances for all study assessments will be followed according to the time window allowances as indicated in the SRM.

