1. Details of liver chemistry stopping criteria and required actions and follow-up assessments after liver stopping or monitoring event are given in Section 8.1.1. All events of ALT $\geq 3 \times$ upper limit of normal (ULN) and bilirubin $\geq 2 \times$ ULN (>35% direct bilirubin) or ALT $\geq 3 \times$ ULN and international normalized ratio (INR) >1.5, if INR measured, which may indicate severe liver injury (possible Hy's Law), must be reported as an SAE (excluding studies of hepatic impairment or cirrhosis).
2. Local urine testing will be standard for the protocol unless serum testing is required by local regulation or IRB/IEC.

Analyte results that could unblind the study will not be reported to investigative sites or other blinded personnel until the study has been unblinded or the subject has undergone emergency unblinding.

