12.7. Appendix 7: Liver Safety: Required Actions and Follow-up Assessments

The procedures listed below are to be followed if a participant meets the liver chemistry stopping criteria defined in Section 8.1.1:

- Immediately withdraw the participant from study treatment
- Notify the VH/GSK medical monitor within 24 hours of learning of the abnormality to confirm the participant's study treatment cessation and follow-up.
- Complete the "Safety Follow-Up Procedures" listed below.
- Complete the liver event case report forms. If the event also meets the criteria of an SAE (see [Appendix 4](#)), the SAE data collection tool will be completed separately with the relevant details.

Safety Follow-Up Procedures for participants with ALT \geq 3x ULN:

- Monitor participants weekly until liver chemistries (ALT, AST, alkaline phosphatase, bilirubin) resolve, stabilize or return to within baseline values.

Safety Follow-Up Procedures for participants with ALT \geq 3xULN and total bilirubin \geq 2xULN (>35% direct bilirubin); or ALT \geq 3x ULN and INR1 > 1.5:

- This event is considered an SAE (see [Appendix 4](#)). Serum bilirubin fractionation should be performed if testing is available. If fractionation is unavailable, urinary bilirubin is to be measured via dipstick (a measurement of direct bilirubin, which would suggest liver injury).
- Make every reasonable attempt to have participants return to the clinic within 24 hours for repeat liver chemistries, additional testing, and close monitoring (with specialist or hepatology consultation recommended).
- Monitor participants twice weekly until liver chemistries (ALT, AST, alkaline phosphatase, bilirubin) resolve, stabilize or return to within baseline values.

In addition, for all participants with ALT \geq 3x ULN, every attempt must be made to also obtain the following:

- Viral hepatitis serology including: Hepatitis A IgM antibody, Hepatitis B surface antigen and Hepatitis B Core Antibody (IgM), Hepatitis C RNA, Cytomegalovirus IgM antibody, Epstein-Barr viral capsid antigen IgM antibody (or if unavailable, obtain heterophile antibody or monospot testing), Hepatitis E IgM antibody.

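### At an isolated ALT of 3×ULN or more, Protocol Section 8.1.1 leaves stopping to the investigator while Appendix 7 orders immediate withdrawal on the same trigger

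*Protocol*

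**What the plan says.** Section 8.1.1 of the Protocol holds the individual liver stopping criterion. Its operative sentence reads: "Discontinuation of study treatment for abnormal liver tests should be considered by the investigator when a participant has an ALT" of 3×ULN or more. The same sentence lets the investigator consider stopping whenever that would serve the participant best. The section then refers to Appendix 7 for the details of follow-up.

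Appendix 7 opens: "The procedures listed below are to be followed if a participant meets the liver chemistry stopping criteria defined in Section 8.1.1". The first action listed is "Immediately withdraw the participant from study treatment". Telling the medical monitor within 24 hours comes next, so that cessation of treatment can be confirmed. The first follow-up block covers ALT ≥3×ULN with no bilirubin or INR condition. A second block covers ALT ≥3×ULN with bilirubin ≥2×ULN (>35% direct) or INR >1.5, and classes that as a serious adverse event.

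Note 1 to the laboratory table in Appendix 2 says: "Details of liver chemistry stopping criteria and required actions and follow-up assessments after liver stopping or monitoring event are given in Section 8.1.1".

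**The concern.** One laboratory value gives two instructions of different force. This is a stopping rule for individual healthy volunteers, who by Section 3.3.2 gain no medical benefit, so it should not depend on which page the site reads.

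The entry criteria show how large a rise is involved. Section 6.2 excludes "Alanine transaminase (ALT) >1.5x upper limit of normal (ULN"), so a participant at 3×ULN has at least doubled from the highest ALT allowed at entry. Section 8.1.1 on its own would still permit daily dosing to continue in Part 2. In Part 1 each period is a single dose, so the question there is whether the participant returns for the next, higher dose about three or four weeks later.

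The SAP (Section 7.2.3.3; Tables 3.20 and 3.47) tabulates liver monitoring and stopping events. Consistent reporting of those events also needs a clear definition of when treatment must stop.

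**Working it through.** The check is a comparison of texts, followed by a count of the doses at stake.

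**1. Same trigger, two actions**

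| Finding | Section 8.1.1 | Appendix 7 | Section 8.1 | Conflict? |
|---|---|---|---|---|
| Isolated ALT ≥3×ULN | Consider stopping | Withdraw at once | Discretionary for laboratory abnormalities | Yes |
| ALT ≥3×ULN with bilirubin ≥2×ULN (>35% direct) or INR >1.5 | Consider stopping | Withdraw at once; serious adverse event | Withdrawal for any serious adverse event | Settled by Section 8.1 |

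The only numerical criterion in Section 8.1.1 is ALT ≥3×ULN, so that is what Appendix 7 refers to when it speaks of meeting the criteria. Its separate block for ALT alone confirms that isolated elevation is covered.

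**2. Does other text decide between them?**

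- Section 8.1 lists withdrawal "At the discretion of the Investigator or the Sponsor for safety (including lab abnormalities or intercurrent illness"), among other grounds. That is discretionary and leaves the question open.
- Section 9 has immediate safety concerns discussed with the sponsor "to determine if the participant will continue or discontinue study treatment". That adds oversight but sets no rule.
- Appendix 2, note 1 sends the reader to Section 8.1.1 for required actions. That section contains none, and it cites Appendix 7 only for follow-up.
- Section 8.1.4 stops a period, a cohort or the escalation. It sets no ALT rule for an individual.
- Section 8.1.2, for QTc, shows how the protocol words a mandatory individual rule: "A participant that meets either bulleted criterion below will be withdrawn from the study".

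No text gives an order of precedence.

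**3. Doses at stake in Part 2**

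Inputs: dosing on Days 1 to 14, and chemistry on Days 2, 4, 6, 8, 10, 12 and 14 (Protocol Section 2, MAD schedule). The highest dose is 320 mg once daily. The full course is 14 × 320 = 4480 mg, which matches SAP Section 6.2.6.

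For first detection on Day d, doses remaining = 14 − d, and milligrams remaining = (14 − d) × 320.

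| Day of sample | Doses remaining | mg remaining at 320 mg |
|---|---|---|
| 2 | 12 | 3840 |
| 4 | 10 | 3200 |
| 6 | 8 | 2560 |
| 8 | 6 | 1920 |
| 10 | 4 | 1280 |
| 12 | 2 | 640 |
| 14 | 0 | 0 |

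This assumes that the sample-day dose is given and the result is back before the next dose. Each further day of turnaround lowers the doses at stake by one. The milligram figures apply only to participants on active drug.

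**4. Threshold against entry limit:** 3 / 1.5 = 2.0-fold.

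**The case against.** The strongest reply is that this is a mismatch of wording with a compliant course always open. Considering discontinuation does not forbid it, so an investigator who withdraws obeys both texts. A reader who follows the references to the end, from Appendix 2 to Section 8.1.1 to Appendix 7, does reach the stricter instruction. The sponsor is consulted on immediate safety concerns, reviews single cases as they arise and has unblinded physicians, so unreviewed dosing is unlikely. No participant is shown to have reached 3×ULN. The preliminary tables list three reports of raised transaminases (two in the SAD, one in the MAD), and every adverse event to that date was Grade 1 or 2. Under Amendment 04, the exposure still to come is Cohort 6 and the remainder of the Expansion Cohort.

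All of that stands as evidence of low likelihood, but it does not remove the conflict. The link from Section 8.1.1 to Appendix 7 is only for follow-up procedures, so a site has no reason to expect a mandatory stop there.

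Appendix 7 could also be read as applying only after the investigator has decided to stop. Its text does not support that: the trigger is meeting the criteria, and its title speaks of required actions. If that reading was intended, Appendix 7 needs rewording instead.

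The QTc rule concerns a different hazard. It shows the drafting style available, not that the ALT rule must match it.

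**Conclusion.** The concern holds. For isolated ALT ≥3×ULN the current protocol gives a discretionary instruction in Section 8.1.1 and a mandatory one in Appendix 7, with nothing to settle the matter. Up to 12 further daily doses (3840 of 4480 mg at 320 mg) could follow under the weaker text, falling to 2 doses (640 mg) for detection on Day 12, given the turnaround and sample-day dosing assumed above. These figures count doses; they do not estimate risk, and how often the situation would arise is unknown.

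The defect is an internal inconsistency in a safety rule. It does not affect endpoints, planned analyses or sample size. It should be corrected because the people exposed are healthy volunteers and the correction is small.

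**What to change.** Reword Section 8.1.1 as: *Study treatment will be discontinued when a participant has an ALT ≥3×ULN.* Keep investigator discretion only for the best-interest clause. Amend note 1 of Appendix 2 to cite Section 8.1.1 for the criterion and Appendix 7 for the required actions.

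The opposite repair, limiting the withdrawal step in Appendix 7 to cases where the investigator has chosen to stop, would also make the texts agree. The mandatory version is preferable because it keeps the protection Appendix 7 already requires.

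The cost is one sentence and one cross-reference, with no change to the SAP, sample size or schedule. The downside is that an occasional participant with a transient isolated rise stops early and cannot resume, since Section 8.1.5.1 bars restart. Section 5.2 allows replacement. MAD escalation needs 14 days of data from at least four active participants, so a cohort with six on active drug can lose 6 − 4 = 2 before a replacement is needed for that purpose.
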